## 5.4.1 Randomization Groups

# 6. STUDY DESIGN

## 6.1. Outline of Procedures

Schedule of Events									
	Screening	Surgery	V	/ound Th	erapy Vis	its	Fo	llow-Up Vi	sits
	Visit 1	Visit 2	Visit 3	Visit 4*	Visit 5*	Visit 6	Visit 7	Visit 8	Visit 9
Procedures	Pre-Op	Surgery	2 Weeks	4 Weeks	6 Weeks	8 Weeks	3 Month s	6 Months	12 Months
ICF/Qualification/	x								
Enrollment	^								
Randomization	Х								
Standard/3D	v		v	v	v	v	v	v	Y
Photographs	^		^	^	^	^	^	^	~
Apply FMTB		Х	Х	Х	Х				
Skin Lab	~			v		v	v	v	v
Measurements	^			^		^	^	^	Λ
Skin Biopsies		Х		Х		Х	Х		Х
Colorimetry	Х		Х	Х	Х	Х	Х	Х	Х
POSAS						Х	Х	Х	Х
Blinded									v
Evaluations									A

\* Visit can be offered as in-person or telehealth visit

## 6.2. Pre-Study Procedures

1. Prior to the start of the study, potential subjects will be screened for eligibility requirements by telephone, e-mail, or in person during their pre-op appointments.

## 6.3. Screening Visit: Visit 1

The purpose of the study, eligibility criteria and potential risks will be discussed with the potential study subject. The following enrollment and screening activities will be performed:

- 1. Candidate subjects will be given an IRB-approved Informed Consent Form (ICF), as detailed in section 5.1, with adequate time for review. The Investigator and/or his designee will address questions and concerns raised by the subject. If the subject agrees, they will sign one copy of the ICF. They will receive a copy, and the original will be kept in the study file.
- 2. Candidate subjects will be screened to ensure they meet all of the study criteria. A brief medical history will be taken and the subject will be questioned about inclusion and exclusion criteria.
- 3. Candidate subjects that sign the initial paperwork will be assigned a screening number.
- 4. After consent has been obtained, the subject will be randomized into one of the treatment groups and all members of the research team will be notified.

- 5. Obtain standard photography.
- 6. Examination of the treatment area by research staff.
- 7. Obtain pre-treatment high-resolution ultrasound images, transepidermal water loss (TEWL) measurements (Bio Aquaflux) and BTC-2000 images.
- 8. Colorimetry assessment of skin in the treatment area using the Pantone SkinTone Guide (STG201).

This visit will take 30-45 minutes

## 6.4. Surgery: Visit 2 (Day 0)

Subjects will arrive for their previously scheduled surgical procedure. A member of the research team may visit with the subject prior to the surgical procedure beginning.

- 1. A clinician will record any changes to the subjects' concomitant medications and will ask subjects if they have experienced any changes in their health since the previous visit. If an adverse event (AE) is reported, then the Investigator will be informed and an AE form will be completed.
- 2. The Principle Investigator will be utilizing the proper wound closure method based on the group the subject was randomized into.
- A total of four skin biopsies will be obtained during the procedure as described in section
  7.3. Two 0.33mm biopsies using a Well-Tech Rapid-Core 0.33mm Biopsy Punch will be obtained from the excised tissue from each breast.

The surgical procedure is expected to take 2-3 hours. Preoperative and intraoperative patient variables recorded by the surgeon will be collected by the research team via chart review to factor into analyses of wound healing and scar quality. These include, but are not limited to: BMI, base width, ptosis grade, nipple to inframammary fold distance, and sternal notch to nipple distance. Intraoperative variables may include, but are not limited to, total anesthesia time and resection weight of each breast.

## 6.4.1 Post-Surgical Procedures

- Subjects will be provided standardized instructions to encourage wound care for a total of 8 weeks.
- Supporting products (dressings etc.) will be provided to ensure compliance and an adequate supply to change dressing before next visits.
- 6.5. Wound Therapy Visits: Visits 3-6 (Weeks 2,4,6 and 8)
  - 1. A clinician will record any changes to the subjects' concomitant medications and will ask subjects if they have experienced any changes in their health since the previous visit. If an adverse event (AE) is reported, then the Investigator will be informed and an AE form will be completed.
  - 2. A clinician will clean and assess wounds. FMTB will be reapplied every two-weeks. If the visit

is being performed virtually, via telehealth, than the patient will be observed while cleaning his/her wound as well as during the reapplication of the FMTBs.

- 3. If in person, photographs will be taken of the wounds as described in section 7.1
- 4. If in person, skin lab measurements will be taken at visits 4 and 6 (weeks 4 and 8) as described in section 7.2.
- 5. If in person, biopsy samples will be obtained at visits 4 and 6 (weeks 4 and 8) as described in section 7.3
- 6. Supporting products will be provided to subject to ensure compliance. If patients opt to have telehealth visits for visits 4 and 6, FMTBs will be provided, as well as alcohol swabs for cleaning the skin. Patients will also be properly trained on how to apply the FMTBs themselves at prior visits if they plan to opt for telehealth visits.

These visits will take about 45 minutes

- 6.6. Follow-Up Visits: Visit 7-9 (Months 3, 6 and 12)
  - 1. A clinician will record concomitant medications and will ask subjects if they have experienced any changes in their health since the previous visit. If an adverse event (AE) is reported, then the Investigator will be informed and an AE form will be completed.
  - 2. Photographs will be taken of the wounds as described in section 7.1
  - 3. Skin lab measurements will be taken during each visit as described in section 7.2
  - 4. Biopsy samples will be obtained as described in section 7.3
  - 5. Patient and Observer Scar Assessment Scale will be completed by both the subject and clinician as described in section 7.4.

These visits will take about 45 minutes

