## 3. CONCISE SUMMARY OF PROJECT

## 3.1. Clinical Study

This is a prospective, within-subject randomized, single blinded study designed to follow up to forty-two (42) qualified and consenting adult females, 18-70 years of age scheduled for elective breast reduction surgery using a standard inverted Wise (inverted "T") incision pattern. The sample size determination of this study is based on a structured power analysis using the observer portion of the Patient and Observer Scar Assessment Scale result as the primary outcome metric. Subjects will be randomized to the method of closure and wound support of the WISE-pattern incisions.

On the intervention side, subjects will have FMTBs applied for final layer closure of the vertical breast incision and, if eligible (incision >5cm in length), final layer closure of the lateral incision. Patients will continue with repeat application every two weeks for ongoing wound support for a total of 8 weeks of therapy. On the control side standard suture closure and wound dressings will be utilized. Patients will be evaluated at two-week intervals up until 8 weeks post-operative, then will have 3 additional follow up visits at 3-months, 6-months and 12-months post-operatively. The effects of the therapy will be analyzed during the follow up visits through photography, skin assessments and POSAS (Patient and Observer Scar Assessment Scale) results.

This is a single-site study at UT Southwestern Medical Center at Dallas in the Department of Plastic Surgery. The Principal Investigator has been selected based on his expertise, qualifications (credentials, training, and medical specialty), subject access, previous clinical research, facilities, and interest in this particular field of research. Subjects will be identified from the clinical practices of Drs. [name], [name], [name] at the University of Texas Southwestern Medical Center. All surgeries for this trial will occur at the Outpatient Building located on the UT Southwestern campus

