## 7. ASSESSMENTS

## 7.1. Photography Procedures

Prior to photography procedures, clinic personnel will ensure that subjects will remove any jewelry and clothing from the area(s) to be photographed and equilibrate for at least 15 minutes to ambient conditions within the clinic before any photographs are taken.

1. Nikon D7200

Standard and close-up photography will be utilized for evaluation of the appearance surgical scars. These photographs will be taken utilizing the Nikon D7200 at screening/baseline, week 2, week 4 (if in-person), week 6 (if in-person), week 8, 3-month post-surgery, 6-months post-surgery and 12-months post-surgery.

2. e-Kare

e-Kare 3D wound management software will be used to obtain high quality 3D wound images in real time that will provide wound dimensions, max depth, surface area and volume.

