## 7.3. Biopsies

Four 0.33mm biopsies, two from each breast scar, will be obtained during multiple visits to assess histological evaluation and gene expression assessment. A subgroup of 10 patients will be selected to participate in the biopsy group. A local numbing agent, 0.5% Lidocaine with epinephrine, will be used to anesthetize the area being biopsied. The biopsy site will be cleaned and marked in the patients file, to keep consistency at all visits.

- Histological assessments will include epidermal and dermal ultrastructure, and immunofluorescence staining of collagen 1, collagen 3, elastin and fibroblast markers associated with fibrosis (smooth muscle actin and Dlk1).
- Gene expression assessment will include collagen and other major extracellular matrix (ECM) molecules and related to scar development.

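### Visit 4 may be done by telehealth even for the 10 biopsy patients, so the only biopsy and skin-lab point between surgery and the end of therapy can be lost

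*Combined protocol and SAP*

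**What the plan says.** **Schedule of Events (section 6.1).** Skin-lab measurements are marked at Visits 1, 4, 6, 7, 8 and 9. Biopsies are marked at Visits 2, 4, 6, 7 and 9. Visits 4 (week 4) and 5 (week 6) carry an asterisk with the footnote "Visit can be offered as in-person or telehealth visit".

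**Section 6.5, items 4 and 5.** Both measures depend on attendance: "If in person, skin lab measurements will be taken at visits 4 and 6 (weeks 4 and 8) as described in section 7.2", and "If in person, biopsy samples will be obtained at visits 4 and 6 (weeks 4 and 8) as described in section 7.3".

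**Section 6.5, item 6.** The choice is described as the patient's, and the visits named differ from the schedule's: "If patients opt to have telehealth visits for visits 4 and 6, FMTBs will be provided".

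**Section 7.3.** "A subgroup of 10 patients will be selected to participate in the biopsy group". For these patients, "Four 0.33mm biopsies, two from each breast scar, will be obtained during multiple visits". The section sets no attendance condition for the subgroup.

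**Section 3.1.** "Patients will continue with repeat application every two weeks for ongoing wound support for a total of 8 weeks of therapy". Week 8 is therefore the end of therapy.

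The documents give no make-up visit, visit window or missing-data rule for week 4.

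**The concern.** On Visit 4 the schedule and section 6.5 agree with each other, so this is not a drafting conflict. The rule as written allows the data to be dropped.

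Week 4 is hard to replace for these two measures. The Visit 2 biopsies come from excised tissue (section 6.4), so week 4 is the first biopsy of the healing scar. It is also the first skin-lab reading after surgery. The next point for both is week 8, when therapy ends. A later visit cannot supply what the tissue looked like while the device was in use.

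The affected outcomes are those listed in section 3.3 as gene regulation, collagen on pathology and skin-lab assessments. A remote visit removes both breasts of that patient from the week-4 comparison. Because the patient may choose, attendance could be related to how healing is going. That is an inference, but if it is so, the week-4 results would describe a selected group.

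**Working it through.** **1. Reproduce the plan's own figure.** Section 2.2 gives 34 patients for d = 0.5 at 80% power. A paired t-test with two-sided alpha 0.05 (assumed, since alpha is not stated) gives 34, and reproduces all 12 cells of that table. For 20% loss, 34 / 0.8 = 42.5, against 42 enrolled; the difference does not matter here. The plan gives no power or precision figure for the biopsy subgroup or the skin-lab measures, so the same test is used for both below.

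**2. Where week 4 sits.**

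| Measure | Scheduled before week 4 | During therapy | End of therapy | Later |
|---|---|---|---|---|
| Biopsy | Surgery (excised tissue) | Week 4 only | Week 8 | Months 3, 12 |
| Skin lab | Pre-operative | Week 4 only | Week 8 | Months 3, 6, 12 |

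Photographs and colorimetry are also marked at week 2, which is not starred, so the statement does not extend to them.

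**3. Biopsy subgroup.** Inputs: 10 patients, four biopsies each per visit (section 7.3), so 40 biopsies at week 4 if all attend. The detectable d solves

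P(T > t(0.975, n−1)) = 0.80, where T is noncentral t with n−1 degrees of freedom and noncentrality d√n.

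The 95% confidence-interval half-width for the mean paired difference is t(0.975, n−1)/√n, in units of the SD of the differences. For n = 10 it is 2.262/√10 = 0.72.

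| Pairs at week 4 | Biopsies | Detectable d | CI half-width (SD) |
|---|---|---|---|
| 10 | 40 | 1.00 | 0.72 |
| 9 | 36 | 1.07 | 0.77 |
| 8 | 32 | 1.16 | 0.84 |
| 7 | 28 | 1.27 | 0.92 |
| 5 | 20 | 1.68 | 1.24 |

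Telehealth uptake q is not in the documents, so a range is assumed, with patients choosing independently. The chance of losing at least one of the 10 is 1 − (1 − q)^10:

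- q = 10%: 65%
- q = 20%: 89%
- q = 30%: 97%
- q = 50%: 99.9%

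The chance of losing five or more (binomial) is 0.2%, 3.3%, 15% and 62% respectively.

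**4. Skin-lab measures.** The starting number is the 42 enrolled. The 20% allowance in section 2.2 is for the trial as a whole and should not all be charged by week 4.

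| Assumed uptake | Pairs at week 4 | Detectable d |
|---|---|---|
| 0% | 42 | 0.44 |
| 30% | 42 × 0.7 = 29.4, taken as 29 | 0.54 |
| 50% | 42 × 0.5 = 21 | 0.64 |

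**5. Which visits may be remote.** The schedule stars Visits 4 and 5. Section 6.5 item 6 names visits 4 and 6. Section 7.1 lists photographs at "week 4 (if in-person), week 6 (if in-person), week 8, 3-month post-surgery", which puts the attendance condition on weeks 4 and 6 and not on week 8, as the schedule does. Visit 4 is open to telehealth on every reading.

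**The case against.** The strongest reply is that this is a disclosed trade-off. The schedule, section 6.5 and section 7.1 all treat week 4 as conditional, and the authors may have accepted optional mid-therapy data in return for convenience. The footnote is permissive, so the site need not offer telehealth to biopsy patients. The subgroup is selected, so willing attenders can be chosen. Inclusion criterion 6 already asks for willingness to return and be evaluated. Consent pages were removed before review, so any attendance terms there cannot be judged.

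Part of this stands: the site has room to protect the data. But nothing written tells it to, and the explicit in-person condition, together with wording that lets patients opt for telehealth, points the other way.

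The limits on the stakes also stand. No section names week 4 as a key time point or plans a test there. With all 10 pairs the subgroup detects only d = 1.00, so it is exploratory in any case, and at 10% to 20% uptake the figure rises only to 1.07 to 1.16.

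Three stronger readings are tempting, and the documents do not support them:

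- **That the primary outcome is at risk.** POSAS starts at week 8 and the blinded photographic evaluation is at 12 months, so a remote Visit 4 touches neither.
- **That the device comparison is biased.** Both breasts drop out together, so the two sides stay balanced. What remains is a question of whom the week-4 result describes.
- **That telehealth should be restricted for everyone.** For the other patients the loss of skin-lab precision is moderate, and the effect of a restriction on their attendance is unknown.

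**Conclusion.** The point holds for the week-4 biopsies and skin-lab measures, as a cheap improvement to secondary outcomes. The plan lets the only such point between surgery and the end of therapy be missed, with no exemption for a subgroup of 10 in which each remote visit costs a tenth of the pairs. Under modest assumed uptake the loss of at least one pair is likely; the loss of half is likely only near 50% uptake.

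The sizes rest on a two-sided 5% paired t-test, independent choices between patients, no other loss by week 4, and uptake rates that are assumed throughout. Selection by state of healing is an inference that the documents neither support nor exclude.

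**What to change.** In the schedule footnote, section 6.5 and section 7.3, state that patients in the biopsy subgroup attend Visit 4 in person, and select the subgroup from patients who agree to this. Telehealth for the other patients can stay as it is.

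In the same edit, reconcile the schedule (Visits 4 and 5) with section 6.5 item 6 (visits 4 and 6). As item 6 reads now, the week-8 biopsies and skin-lab measures could be missed in the same way.

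The cost is a line of text in each place. Ten patients give up telehealth at one visit, and the subgroup may be slightly harder to fill. No procedure is added, because the week-4 biopsies and measurements are already scheduled.

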## 7. ASSESSMENTS

## 7.1. Photography Procedures

Prior to photography procedures, clinic personnel will ensure that subjects will remove any jewelry and clothing from the area(s) to be photographed and equilibrate for at least 15 minutes to ambient conditions within the clinic before any photographs are taken.

1. Nikon D7200

Standard and close-up photography will be utilized for evaluation of the appearance surgical scars. These photographs will be taken utilizing the Nikon D7200 at screening/baseline, week 2, week 4 (if in-person), week 6 (if in-person), week 8, 3-month post-surgery, 6-months post-surgery and 12-months post-surgery.

2. e-Kare

e-Kare 3D wound management software will be used to obtain high quality 3D wound images in real time that will provide wound dimensions, max depth, surface area and volume.

## 7.2. Noninvasive Skin Assessments

Noninvasive measurements are being collected for research purposes only.

- 1. High-Frequency Ultrasonography Ultrasonography will be used to evaluate the skin thickness and density.
- 2. Transepidermal Water Loss (TEWL) TEWL will be used to evaluate the barrier functions of the skin's epidermal layer to determine the progress of epidermal healing.
- BTC-2000
  BTC will be used to measure the skin's laxity, viscoelastic deformation, stiffness, energy absorption, elasticity, and deformation values.

## 7.3. Biopsies

Four 0.33mm biopsies, two from each breast scar, will be obtained during multiple visits to assess histological evaluation and gene expression assessment. A subgroup of 10 patients will be selected to participate in the biopsy group. A local numbing agent, 0.5% Lidocaine with epinephrine, will be used to anesthetize the area being biopsied. The biopsy site will be cleaned and marked in the patients file, to keep consistency at all visits.

- Histological assessments will include epidermal and dermal ultrastructure, and immunofluorescence staining of collagen 1, collagen 3, elastin and fibroblast markers associated with fibrosis (smooth muscle actin and Dlk1).
- Gene expression assessment will include collagen and other major extracellular matrix (ECM) molecules and related to scar development.

## 7.4. Colorimetry

The Pantone SkinTone Guide is a handheld tool consisting of 110 color swatches that realistically mimic human skin tones, with stepwise variations in lightness and undertone. The guide was specifically formulated to be the closest physical representation of skin colors and is the only internationally available color standard to accurately match skin tones. Each SkinTone number is comprised of a four-digit alphanumeric number; the first two numbers reflect the hue or undertone of the skin while the second two represent the tone or lightness and darkness of the skin. This tool will be utilized to establish a clinically acceptable objective assessment for assessing the coloring of patients' scars.

## 7.5. Patient and Observer Scar Assessment Scale (POSAS)

This validated scale will be used to assess the scar quality after surgery from the patient and observer (clinician) prospective.

This scale should be completed in two steps:

- Patient Self-Assessment: Subjects will be asked to visually assess their scar appearance and complete the 10-point scale. The patient scale will include questions regarding pain, itch, thickness, color, stiffness, irregularity, and overall opinion.
- Observer Assessment: Clinician will visually assess the scar appearance during the visit and complete the 10-point scale. The observer scale will include items with subcategories related to

vascularity, pigmentation, relief/texture, thickness, pliability, surface area and overall opinion.

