## 2.2. Sample Size/Power Analysis Factors:

The sample size calculation will be determined by the primary outcome: POSAS-O score. The study will enroll 42 patients which will allow us to detect a moderate effect (Cohen's d=0.5) in scar quality measured by POSAS-O with at least 80% power, accounting for an estimated 20% loss of patients.

In a study evaluating the effect of platelet-rich plasma glue on surgical scars following breast reduction mammoplasty, the control group had a mean POSAS-O score of 20.4 (SD 12.5) at 1-year. Although a minimal

clinically important difference (MCID) for POSAS has not been established in the literature, Cohen's d effect size (0.2 represents "small" effect, 0.5 represents "moderate" effect, 0.8 represents "large" effect) can be used to estimate a difference that may be clinically important.

	Effect Size (Cohen's d)			
	0.2	0.3	0.4	0.5
Change in POSAS-O score	2.5	3.75	5	6.25
Proportional change to	4.2%	6.3%	8.3%	10.4%
maximum POSAS-O score				

	Effect Size (Cohen's d)			
Power	0.2	0.3	0.4	0.5
80%	199	90	52	34
85%	227	102	59	38
90%	265	119	68	44

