## 3.2. Primary Outcomes

- Patient and Observer Scar Assessment Scale (POSAS)
- Photographic Assessment

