## 5.4. Randomization

Randomization via www.randomizer.org computer-based method: sealed pre-numbered randomization envelopes will be provided and opened by research staff and used to obtain randomization assignment. Unmasking of randomization assignment will occur after all portions of the surgical procedure are complete excepting only final skin layer closure and with intraoperative procedural symmetry confirmed.

Group 1				
Side 1	Side 2			
Final layer dermal closure with poliglecaprone 25	Final layer closure with force modulating tissue			
suture (Monocryl ® , Ethicon, Inc. Bridgewater, NJ)	bridges (FMTB) (Brijjit BP100-6, Brijjit Medical Inc.,			
	Marietta, GA)			
Group 2				
Side 1	Side 2			
Final layer closure with force modulating tissue	Final layer dermal closure with poliglecaprone 25			
bridges (FMTB) (Brijjit BP100-6, Brijjit Medical Inc.,	suture (Monocryl ® , Ethicon, Inc. Bridgewater, NJ)			
Marietta, GA)				

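### Nothing in the plan requires the clinician who scores POSAS-O, the outcome that sets the sample size, to be masked to side or non-treating

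*Combined protocol and SAP*

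**What the plan says.** Section 2.2 states: "The sample size calculation will be determined by the primary outcome: POSAS-O score". Section 3.1 repeats that the power analysis rests on the observer part of the scale. Appendix I defines the score as the sum of six items, each rated 1 to 10. Pliability is judged by handling the scar.

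On who rates, section 7.5 says: "Clinician will visually assess the scar appearance during the visit and complete the 10-point scale". Section 6.6 step 5 has the scale completed by the subject and a clinician at months 3, 6 and 12, and the schedule in 6.1 adds week 8. None of these places says whether the clinician knows the side or has treated the patient.

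On blinding, section 3.1 opens: "This is a prospective, within-subject randomized, single blinded study". It does not say who is blinded. Section 7.6 does specify masked, non-treating assessors, but only for three surgeons reading 12-month photographs. The schedule in 6.1 lists those blinded evaluations at Visit 9 only, in a separate row from POSAS (Visits 6 to 9). Section 3.2 lists "Photographic Assessment" as a primary outcome beside POSAS.

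On who knows the side, section 6.4 step 2 says that the surgeon "will be utilizing the proper wound closure method based on the group the subject was randomized into". Under 6.5 step 2, a clinician cleans and assesses the wounds at the two-weekly visits where the device is reapplied.

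**The concern.** The outcome that determines the number of patients is a judgement made at the bedside, and the plan leaves open who makes it. The surgeon who closed the two breasts differently knows the side. So does anyone who reapplies devices to one breast during the eight weeks of therapy. Nothing bars either from scoring POSAS-O.

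Each patient is her own control, so patient-level nuisance factors cancel in the within-patient difference. A rater's expectation about the device does not cancel, because it follows the treatment and not the patient. Randomizing the side does not remove it, and enrolling more patients does not shrink it. A positive POSAS-O result could then be hard to separate from rater expectation. Masking cannot be added once the scores have been collected.

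**Working it through.** **1. Who could be the blinded party?** The surgeon learns the side at closure (5.4, 6.4). The patient may reapply the devices herself under observation at a telehealth visit (6.5), so she cannot be assumed masked. That leaves the photograph readers, whom 7.6 masks explicitly, and the clinic rater of POSAS-O, on whom the plan is silent. The single-blind label is satisfied by the photograph readers alone, so it does not settle the status of the POSAS-O rater.

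**2. Reproducing the plan's sample size.** Section 2.2 gives d = 0.5, 80% power, 34 patients before dropout and 42 enrolled with 20% loss. Alpha and sidedness are not stated. A paired t-test by noncentral t at two-sided alpha 0.05 reproduces all 12 cells of the table (80% row: 199, 90, 52, 34), with 80.8% power at n = 34. A one-sided test gives 27 at d = 0.5 and a normal approximation gives 32, so two-sided 0.05 is a reasonable assumption. Dropout: 34 / (1 − 0.20) = 42.5, against the stated 42. Masking the rater does not change this number.

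**3. What a consistent lean would do (illustration only).**

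Inputs from 2.2: n = 34 and SD 12.5. Assumed: two-sided alpha 0.05, no true effect, and correlation r between the two breasts.

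- SD of differences = 12.5 × √(2(1 − r)). At r = 0.5 this is 12.50. At r = 0.3 and 0.7 it is 14.79 and 9.68.
- SE = SD of differences / √34 = 2.144 at r = 0.5 (2.536 and 1.661 at r = 0.3 and 0.7).
- Smallest significant difference = t(0.975, 33) × SE = 4.36 points (5.16 and 3.38).
- The probability of a significant result favouring the device comes from the noncentral t with 33 df and noncentrality shift / SE.

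| Shift (points) | Per item (shift / 6) | Share of 60-point maximum | r = 0.3 | r = 0.5 | r = 0.7 |
|---|---|---|---|---|---|
| 0 | 0 | 0 | 2.5% | 2.5% | 2.5% |
| 1 | 0.17 | 1.7% | 5.7% | 6.6% | 8.5% |
| 2 | 0.33 | 3.3% | 11.6% | 14.6% | 21.5% |
| 3 | 0.50 | 5.0% | 20.9% | 27.4% | 41.8% |

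Simulation with 200,000 runs per cell agrees to within 0.2 percentage points. None of these shifts reaches the significance threshold by itself. At r = 0.5 they supply 1/4.36 = 23%, 2/4.36 = 46% and 3/4.36 = 69% of it.

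**4. Do the photographs cover the gap?** Only in part. They are masked and listed as primary, but the trial is not powered on them, they exist as masked reads at 12 months only, and a photograph cannot assess pliability.

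**The case against.** The strongest reply is that the point rests on silence. No section says that the POSAS-O rater is unmasked, is the surgeon, or reapplies devices, and the single-blind label is not limited to photographs. A reader might infer that scoring will be unmasked; the documents do not show that. What they show is that nothing prevents it, while the explicit requirement is written for the photograph readers and listed in a separate schedule row.

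Second, a listed primary outcome already has masked, non-treating assessors, and 7.6 gives that read the task of judging whether the device works. This stands, and it limits the damage, since a POSAS-O difference can be compared with it. It does not protect the powered outcome.

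Third, masking appears elsewhere: section 5.4 says "Unmasking of randomization assignment will occur after all portions of the surgical procedure are complete excepting only final skin layer closure". That is concealment up to closure. It ends in the operating room and has no bearing on scoring months later.

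Fourth, 6.3 step 4 says that after consent "the subject will be randomized into one of the treatment groups and all members of the research team will be notified". It is tempting to read this as releasing the side to everyone at Visit 1, in contradiction of 5.4. The text does not say what is notified; notice that the patient has been randomized would fit with 5.4. Under either reading the surgeon learns the side by closure, so this is a lesser clarification and not evidence about the rater.

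Fifth, the shift sizes and correlations have no source in the documents. That is correct. The table shows sensitivity to a lean if one exists; it is not an expected error rate for this trial.

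**Conclusion.** The concern holds as a gap in specification with real consequences: the powered, subjective outcome has no requirement for a masked or non-treating rater, and the blinding label does not name who is blinded. It does not extend to a claim that POSAS-O will be scored unmasked.

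The size of any bias is unknown. Under the stated assumptions (34 pairs, SD of differences 12.5, two-sided alpha 0.05, no true effect), a consistent lean of one third of a point per item would raise the chance of a false positive favouring the device from 2.5% to 14.6%, or 11.6% to 21.5% over r = 0.3 to 0.7. A small lean is therefore enough to matter, and the protection is cheap relative to that exposure.

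**What to change.** - **6.6 and 7.5:** have POSAS-O scored, at least at 12 months, by an existing study clinician who did not operate on or reapply devices for that patient and is not told the side. Ask the patient not to disclose it. Label week-8 scores as unmasked if the side is visible then.
- **3.1:** state who is masked, and that the patient scale is not masked.
- **Fallback:** if existing staff cannot provide such a rater, describe POSAS-O as unmasked and interpret it alongside the masked 12-month A/B and Manchester reads already planned. This discloses the bias; it does not remove it.
- **Separate, lesser clarification in 6.3 step 4:** say that the team is told that randomization has taken place, but not the side, before the point given in 5.4.

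The cost is wording, with no new assessment and no change to the sample size. The practical downside is that some visits need a particular team member. Section 3.1 says "Subjects will be identified from the clinical practices of" more than one surgeon, so a clinician who did not operate on the patient may be available. The documents do not describe follow-up staffing, so this is not assured.
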